02.05.2018

Title

Treatment of Newly Diagnosed Gastroesophageal Reflux Disease in a National Population-based Cohort

Aim

To compare rate of surgery with medical treatment in patients with newly diagnosed gastro-esophageal reflux disease in a nationwide population based cohort over 15 years.

Background

Episodic reflux of gastric contents to the esophagus is physiological but is considered gastroesophageal reflux disease (GERD) when accompanied by bothersome symptoms, typically heartburn, regurgitation or retrosternal pain. Extra-esophageal symptoms such as asthma, laryngitis and chronic cough may also occur (1). GERD is a complex and multifaceted disease (2, 3), affecting 10-20% of the Western population (4) and has been shown to significantly reduce the quality of life (5). Worldwide, the prevalence of GERD has been increasing (6–8). Treatment of GERD consists of anti-secretory drugs, mainly proton pump inhibitors (PPI), or anti-reflux surgery. Laparoscopic anti-reflux surgery is considered standard of care in surgical treatment of gastro-esophageal reflux disease (9) and with careful patient selection based on thorough preoperative workup (10), symptom control and patient satisfaction are high compared to medical therapy. This has previously been demonstrated in metaanalysis (11, 12).

From 1990-2000 the utilization of anti-reflux surgery in the USA rose to 16.7 procedures per 100.000 inhabitants with a concomitant rise in the use of the transabdominal laparoscopic approach. This resulted in a decline of perioperative mortality and morbidity (13, 14). The rate of anti-reflux surgery dropped to 6.1 procedures per 100.000 inhabitants in 2010, when the patients were now older with significantly higher levels of comorbidity. Despite this, length of stay, morbidity and mortality was reduced even further. The laparoscopic approach is used in 80% of American procedures and the rate has not changed during the last ten years. It is unknown whether Denmark follows the same trends, as the popularity of anti-reflux surgery has been somewhat limited and the surgical setup is different with significantly fewer centers. In a Danish study, investigating the rate of reoperative anti-reflux surgery from 1997-2005, the rate of primary surgery was 5.2 per 100.000 inhabitants with a reoperation rate of 5% (15), however no data has been presented after 2005, and no Danish study has focused on treatment of newly diagnosed patients suffering from reflux disease.

As such, it is currently unknown how many patients each year are given the diagnosis GERD after upper endoscopy in Denmark and what treatment they receive. It is also unknown how the utilization of medical and surgical treatment has developed in this group of patients.

Methods

The study is a register-based cohort study with data from Danish national health registries (The National Patient Registry, The Danish National Prescription Register and The Civic Registry). The study period is 2000-2015.

The study population consists of all adult Danish patients diagnosed with GERD and GERD-related diagnosis identified with ICD-10 codes DK20.9B, DK21.0-21.9B & DK22.7 using The National Patient Registry).To

02.05.2018

validate GERD-diagnosis, upper endoscopy must have been performed no more than three months before time of diagnosis for the patient to be included. Endoscopy must have been performed during the study period 2000-2015.

Patients with GERD and GERD-related diagnosis up to four years before upper endoscopy are excluded from the study as are patients with any diagnosis of cancer of the gastrointestinal tract 4 years prior to upper endoscopy to the end of follow-up.

Age, sex and Charlson Comorbidity Index at date of primary upper endoscopy are derived from the National Patient Registry. From the same source, any anti-reflux surgery (Nomesco: KJBC00, KJBC01, KJBC02, KJBW96, KJBW97) performed within two years of inclusion are identified.

From The National Prescription Register, data on medical treatment with any antacid and anti-secretory treatment (ATC: MA02B) are identified from 4 years before inclusion to 2 years after. Data on anti-thrombotic drugs and non-steroid anti-inflammatory drugs (ATC: MB01A & MM01A) are also retrieved for the same period to adjust for possible preventive therapy with anti-secretory drugs. From the Civic Register, data on mortality in the follow-up period are retrieved.

Statistical analysis

Data will be analyzed using STATA15. Descriptive analysis of age, sex, Charlson Comorbidity Index, mortality and rate of anti-thrombotic treatment comparing patients treated pharmacologically (in defined daily dosages per year) or surgically (any anti-reflux procedure) for reflux disease using Student's t-test, Chi2-test and Mann-Whitney-U test.

Logistic and multinomial regression will be performed with treatment type (pharmacological, surgical or none) as primary outcome and age, sex, Charlson Comorbidity Index, pharmacological anti-reflux treatment prior to diagnosis, antithrombotic treatment and year of diagnosis as independent variables.

Secondary analysis will be performed using Cox-regression investigating time to initiation of any treatment with age, sex, Charlson Comorbidity Index, pharmacological anti-reflux treatment prior to diagnosis, antithrombotic treatment and year of diagnosis as independent variables. Change in treatment rates over time will also be investigated using national Danish census data and Poisson regression.

Sensitivity analysis excluded patients with anti-thrombotic treatment will be performed.

Funding and Ethical considerations

The study is part of a ph.d. thesis and is funded by The Region of Southern Denmark, The University of Southern Denmark, The Department of Surgery, Kolding Hospital and The Research Council at Little Belt Hospital.

The study requires no informed consent in Danish law as the study is register-based. However, permission from The Danish Data Protection Agency and The Danish Health Data Agency will be obtained before the study is commenced.

None of the involved parties have financial interests or conflicts of interest pertaining to this study.

References

1. Madanick RD. Extraesophageal presentations of GERD: where is the science? *Gastroenterol Clin North Am.* 2014;43:105-120.

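### A GERD code first recorded at the anti-reflux operation can qualify a patient, so one route into the treatment-type analysis depends on the outcome

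*Combined protocol and SAP*

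**What the plan says.** All of the following is in the Methods section unless stated.

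- **Qualifying code.** Patients are "identified with ICD-10 codes DK20.9B, DK21.0-21.9B & DK22.7 using The National Patient Registry". No contact type is specified.
- **Link to endoscopy.** The only link is timing: "upper endoscopy must have been performed no more than three months before time of diagnosis for the patient to be included".
- **Washout.** "Patients with GERD and GERD-related diagnosis up to four years before upper endoscopy are excluded from the study". It looks back from the endoscopy, so it cannot remove a first GERD code made at an operation after that endoscopy.
- **Surgery.** "From the same source, any anti-reflux surgery (Nomesco: KJBC00, KJBC01, KJBC02, KJBW96, KJBW97) performed within two years of inclusion are identified". The source is the National Patient Registry, which also supplies the qualifying code.
- **Drug treatment.** "From The National Prescription Register, data on medical treatment with any antacid and anti-secretory treatment (ATC: MA02B) are identified". This is a separate register, and a prescription in it creates no qualifying diagnosis code.
- **Index date.** Covariates are taken at the first endoscopy: "Age, sex and Charlson Comorbidity Index at date of primary upper endoscopy are derived from the National Patient Registry". Surgery is counted from inclusion, which is not tied to either the endoscopy date or the diagnosis date.

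Under Statistical analysis, treatment type (drug, surgery or none) is the primary outcome of the logistic and multinomial models. Year of diagnosis is a covariate in these and in the Cox model for time to any treatment. Trends in treatment rates are also to be studied by Poisson regression with census data. The only sensitivity analysis concerns anti-thrombotic treatment.

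**The concern.** Take two patients with the same endoscopy, neither given a GERD code at that contact. One is operated within three months and receives a GERD code on the operation contact. That patient enters, and is classed as surgical. The other is sent home with a prescription or nothing, and does not enter unless some other hospital contact records GERD. Whether a patient is in the denominator then depends on the treatment received. The Background describes surgery as performed "with careful patient selection based on thorough preoperative workup", so an endoscopy shortly before an operation is plausible.

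The comparison of surgery with medical treatment is the study's aim. If endoscopies are incompletely coded, this route adds operated patients whose unoperated counterparts are missing. If coding completeness shifts between 2000 and 2015, the surgery share can shift with no change in practice, and the year coefficients would absorb it. No planned analysis would reveal either effect.

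**Working it through.** The documents give no expected surgery share, coding completeness or time from endoscopy to operation, so there is no stated figure to reproduce. The model below is illustrative and all its inputs are assumed.

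**Inputs**
- p: true two-year surgery share among newly endoscoped GERD patients, set at 2%.
- u: share of these patients with no GERD code from the endoscopy or any other non-operative contact within three months, set at 10% or 30%.
- q: share of operations that fall within three months of an endoscopy, set at 0.3, 0.6 or 1.

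**Formula, per true case**
- Operated patients in the cohort: p(1−u) + upq.
- All patients in the cohort: (1−u) + upq.
- Observed share: the first divided by the second.

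The term upq is the operation-contact route. It adds the same amount to numerator and denominator, so it can only raise a share that is below 1. It vanishes if u = 0 or q = 0.

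| u | q | Operated | Entrants | Observed share | Relative change |
|---|---|---|---|---|---|
| 10% | 0.3 | 0.0186 | 0.9006 | 2.07% | +3% |
| 10% | 0.6 | 0.0192 | 0.9012 | 2.13% | +7% |
| 30% | 0.3 | 0.0158 | 0.7018 | 2.25% | +13% |
| 30% | 0.6 | 0.0176 | 0.7036 | 2.50% | +25% |
| 30% | 1 | 0.0200 | 0.7060 | 2.83% | +42% |

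For small p the relative change is close to uq/(1−u), so the choice of 2% matters little.

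**Trend in the share, p fixed at 2%.** If u falls from 30% to 10% at q = 0.6, the observed share goes from 2.50% to 2.13%. The ratio is 0.02130/0.02501 = 0.85, a false fall of 15%. At q = 0.3 the ratio is 0.02065/0.02251 = 0.92, a false fall of 8%. If u rises instead, the false trend is upward.

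**With operation-contact codes disallowed.** The share becomes p(1−u)/(1−u) = p for any u and q. This holds only if being coded is unrelated to later surgery.

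**Operations per inhabitant.** Here the denominator is the census, so only the numerator matters. With q = 0.6 and u falling from 30% to 10%:
- Current rule: 0.0176 to 0.0192 counted operations per true case, a false rise of 9%.
- Operation-contact codes disallowed: p(1−u) goes from 0.0140 to 0.0180, a false rise of 29%.

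The same exclusion that cleans the share makes the population rate more dependent on coding.

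**The case against.** **Direction.** The strongest objection is that one route upward does not establish a net bias upward. A surgical candidate coded GERD at referral, before a preoperative endoscopy, is removed by the four-year washout. That lowers the share if such candidates are coded before endoscopy more often than other patients. This stands. A reader might infer that the reported surgery share will be too high overall, but the documents do not support that.

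**Likelihood.** A thorough workup also means hospital contacts before the operation at which GERD would be coded, so a first code at the operation may be uncommon. The model gives operated and unoperated patients the same u. In addition, dating covariates at the first endoscopy suggests that endoscopy, workup and operation must all fit into three months, which favours a low q. This stands as a reason to expect the lower part of the table. The row with q = 1 would need every operation in the two-year window to fall within three months of an endoscopy, so it is an extreme and not an estimate.

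**Trend.** Nothing in the documents says that coding completeness or time to surgery changed over the study period. A reader might infer that a falling surgery share would be an artefact, but that is conditional on a change that is not shown.

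**Time to event.** It is tempting to say that these patients have zero time to surgery. That holds only if time starts at diagnosis. If it starts at endoscopy, the operation comes at some point within three months. The Cox outcome is time to any treatment, so a prescription may also come first.

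**Remedy.** A code from a surgical outpatient visit would still qualify, although a patient never referred has no such visit. Operated patients also have less time than others to acquire a code before their operation. Both points stand and shape the fix.

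None of this closes the route itself.

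**Conclusion.** The point holds as a defect in the entry rule. The rule lets the operation supply both eligibility and the surgical outcome, and a prescription cannot do the same. Within the logistic, multinomial and Cox analyses this route acts in one direction, towards more surgery among included patients. Its size cannot be found from the documents. It is about +3% relative at u = 10% and q = 0.3, and about +25% at u = 30% and q = 0.6, with p = 2% and equal coding in operated and unoperated patients. It may be negligible if endoscopies are well coded.

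The point does not extend to the census-based rates. Operations counted per inhabitant are real and are not inflated through a missing denominator, although which operations are counted still depends on coding.

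**What to change.** 1. Define the index date as either the endoscopy or the diagnosis, and use it for the window in which surgery "performed within two years of inclusion are identified" and for the start of time in the Cox model.
2. For the logistic, multinomial and Cox analyses, require the qualifying GERD code to come from the endoscopy contact, or from another contact that starts before any listed operation. State that the operation contact itself does not count, even when admission precedes the operation date or the endoscopy is done on the same contact.
3. Report by year of diagnosis how many patients have their first GERD code on the operation contact.
4. Repeat these analyses with those patients included.
5. Do not apply the exclusion to the Poisson rates of operations per inhabitant.

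Diagnoses, procedures and their dates come from one register, so the cost is a few sentences in the plan and one repeat of each model.

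The downside is that some rapid operations in truly new patients leave the main share analysis. Operated patients also have less time to acquire a qualifying code, a small bias towards less surgery. For these two mechanisms, the main and repeat analyses bracket the answer. Counting only the endoscopy contact's code avoids the shorter coding time and also the codes from surgical outpatient visits, but loses patients whose diagnosis is first recorded at a later visit. If the yearly counts are negligible, the sponsor can report that and the matter is closed.

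### The GERD look-back runs up to the endoscopy date, so new patients coded both during work-up and again after endoscopy are excluded as previously diagnosed

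*Combined protocol and SAP*

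**What the plan says.** The Methods section sets two eligibility windows, both tied to the upper endoscopy.

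- **Inclusion.** The plan requires that "upper endoscopy must have been performed no more than three months before time of diagnosis for the patient to be included". The qualifying code therefore falls on the day of endoscopy or in the three months after it.
- **Exclusion.** "Patients with GERD and GERD-related diagnosis up to four years before upper endoscopy are excluded from the study". No gap before the endoscopy is stated.

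The diagnosis is any listed code, "identified with ICD-10 codes DK20.9B, DK21.0-21.9B & DK22.7 using The National Patient Registry". There is no restriction by type of contact, and nothing separates a working diagnosis from a confirmed one.

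The Aim concerns "patients with newly diagnosed gastro-esophageal reflux disease in a nationwide population based cohort over 15 years". The end of the Background gives the gap to be filled: "it is currently unknown how many patients each year are given the diagnosis GERD after upper endoscopy in Denmark". Baseline covariates are taken at the endoscopy: "Age, sex and Charlson Comorbidity Index at date of primary upper endoscopy are derived from the National Patient Registry". The Statistical analysis section plans one sensitivity analysis, which concerns anti-thrombotic treatment and does not vary the look-back.

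**The concern.** A look-back is meant to remove patients whose disease was known before the current episode. Because this one ends at the endoscopy, it also catches codes that belong to the current episode. A patient coded with GERD at a hospital clinic, scoped a few weeks later and coded again is treated as an old case. The same patient sent straight to endoscopy is kept. Entry then depends partly on when an administrative code was entered, and not only on whether the disease is new.

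Three results are exposed: the number of new patients per year, the split between surgical, drug and no treatment (the primary outcome of the regression models), and the effect of year of diagnosis. If clinic coding or referral practice changed over 2000-2015, the number removed would change with it, and the change could appear as a time trend.

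**Working it through.** The plan states no figure on this point, so there is none to reproduce. The check is first a timeline and then a sensitivity range.

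**Timeline, with endoscopy at day 0.** Inclusion needs a GERD code from day 0 to about day +90. Exclusion applies to any GERD code in the four years before day 0.

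| Patient | Code before endoscopy | Code after endoscopy | Inclusion met | Exclusion met | Result |
|---|---|---|---|---|---|
| A | day -21 | day +7 | yes | yes | out |
| B | day -21 | none | no | yes | out under either rule |
| C | none | day +7 | yes | no | in |

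A and C can be the same new disease episode. The look-back is the deciding rule only for A. B is lost through the inclusion rule whatever the look-back says.

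**Size.** Both inputs are assumptions, because the documents give no counts and no data on code timing.

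- p is the share of otherwise eligible new patients coded both before endoscopy (same work-up) and within three months after it: 5%, 10% or 20%.
- r is the frequency of anti-reflux surgery in these patients relative to the rest: 0.5, 1, 2 or 3.

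The cohort count is low by p. If s is the surgical proportion in the patients kept, the proportion with everyone included is s × ((1 - p) + p × r). The relative error of the reported proportion is therefore 1/((1 - p) + p × r) - 1.

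| p | r = 0.5 | r = 1 | r = 2 | r = 3 |
|---|---|---|---|---|
| 5% | 1/0.975 - 1 = +2.6% | 0 | 1/1.05 - 1 = -4.8% | 1/1.10 - 1 = -9.1% |
| 10% | 1/0.95 - 1 = +5.3% | 0 | 1/1.10 - 1 = -9.1% | 1/1.20 - 1 = -16.7% |
| 20% | 1/0.90 - 1 = +11.1% | 0 | 1/1.20 - 1 = -16.7% | 1/1.40 - 1 = -28.6% |

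These are relative errors, not percentage points.

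**Trend.** If p is constant over the years, the relative error is constant and creates no trend in the proportion. Suppose instead that p rose from 5% to 20% with true practice unchanged. At r = 2 the reported proportion would change by the factor 1.05/1.20 = 0.875, an apparent fall of 12.5%. At r = 0.5 the factor is 0.975/0.90 = 1.083, an apparent rise of 8.3%.

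**Rates per inhabitant.** If the planned census-based Poisson analysis counts operations within this cohort, the removed patients' operations leave the numerator while the population denominator stays. The shortfall is p × r/((1 - p) + p × r). At p = 10% this is 0.10/1.00 = 10% for r = 1, 0.20/1.10 = 18% for r = 2 and 0.30/1.20 = 25% for r = 3.

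**The case against.** The best defence is that the strict rule is deliberate. The Background describes patients who receive the diagnosis after endoscopy, and the endoscopy requirement is there to validate the diagnosis. Removing anyone who already carries a code is a conservative definition of new disease. This explains why a post-endoscopy code is required, and that requirement should stay. It does not explain the removal of patient A, who also received the diagnosis after endoscopy. The plan neither states nor justifies that work-up codes count as prior disease.

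It is also fair to say that nothing in the documents shows the problem to be common. They do not report how often clinics enter a GERD code before endoscopy, how often such patients are coded again, whether they have more surgery, or whether referral changed. This stands, and it is why only a range can be given.

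The effect on counts alone is secondary. The Aim compares treatments, and no analysis of diagnosis incidence is planned. This stands too, although the annual number is part of the stated knowledge gap and census-based treatment rates are planned.

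One could read the exclusion phrase as ending four years before endoscopy. That would keep recently diagnosed patients in a cohort meant to be newly diagnosed, so it is not a sensible reading.

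**Conclusion.** The point holds for patients coded in the same work-up on both sides of the endoscopy. The written rule misclassifies them, and no other part of the plan corrects or reveals this. Under the assumed shares the cohort is short by 5-20%. The relative error in the surgical proportion runs from about 3-11% overstatement at r = 0.5, through none at r = 1, to 5-29% understatement at r = 2-3. The change is worth making because it is cheap; the true size is unknown.

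A reader might infer three stronger claims that the documents do not support:

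- **Every new patient coded before endoscopy is lost through the look-back.** Those not coded again fail the inclusion rule in any case, so p is the smaller, twice-coded group.
- **The surgical proportion is understated.** It would be if clinic-first patients have more surgery, but the documents do not say so, and r below 1 reverses the sign.
- **Excluded patients return years later as new cases with a wrong index year.** The plan says such patients are excluded from the study and refers to a primary endoscopy, which suggests one index event per patient. Re-entry is not a stated rule.

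**What to change.** 1. Exclude patients with a GERD or GERD-related code from four years to three months before endoscopy. A code in the last three months counts as part of the index episode. This mirrors the plan's own three-month window.
2. Keep the requirement of a GERD code on or within three months after endoscopy, so that every case remains endoscopy-verified.
3. For the readmitted patients, use the endoscopy as the single index date, both for the year variable and as the time origin of the Cox model. Count anti-reflux drugs as treatment before diagnosis only up to the first code of the episode. State how prescriptions filled between that code and the endoscopy are handled, since they would otherwise be neither prior treatment nor follow-up.
4. Report the strict look-back as a sensitivity analysis, with the number of patients who change status in each calendar year. A small and stable number shows that the choice does not matter.

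**Cost.** No new data are needed, because applying the look-back already requires dated GERD codes before endoscopy. The work is a changed eligibility rule, the date definitions in step 3 and one extra run. A few older cases whose earlier contacts were never coded may enter; the sensitivity analysis shows their effect together with that of the new cases. Entry will still depend partly on whether a patient is coded again after endoscopy, and the report should say so.

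### NSAID data are retrieved to adjust for preventive anti-secretory therapy, but no planned analysis names NSAIDs; only antithrombotic treatment is carried through

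*Combined protocol and SAP*

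**What the plan says.** **Retrieval (Methods).** Medical treatment is taken from the prescription register as "data on medical treatment with any antacid and anti-secretory treatment (ATC: MA02B"; these prescriptions "are identified from 4 years before inclusion to 2 years after". No indication is required. For anti-thrombotics, coded MB01A, and for NSAIDs, coded MM01A, one purpose is given: "non-steroid anti-inflammatory drugs (ATC: MB01A & MM01A) are also retrieved for the same period to adjust for possible preventive therapy with anti-secretory drugs".

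**Population (Methods).** The GERD diagnosis must be supported by endoscopy: "upper endoscopy must have been performed no more than three months before time of diagnosis for the patient to be included".

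**Analyses (Statistical analysis).**
- The descriptive comparison ends its list with "mortality and rate of anti-thrombotic treatment comparing patients treated pharmacologically (in defined daily dosages per year".
- The logistic and multinomial models, with treatment type as primary outcome, end their list with "pharmacological anti-reflux treatment prior to diagnosis, antithrombotic treatment and year of diagnosis as independent variables".
- The Cox model is described as "investigating time to initiation of any treatment with age, sex, Charlson Comorbidity Index, pharmacological anti-reflux treatment prior to diagnosis, antithrombotic treatment", followed by year of diagnosis.
- The Poisson analysis of trends lists no covariates.
- The remaining analysis reads "Sensitivity analysis excluded patients with anti-thrombotic treatment will be performed".

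**The concern.** The plan itself recognises that some patients receive anti-secretory drugs to protect against the effects of another drug, and it names two drug classes for which this must be handled. Only one of them reaches the analyses. A patient given an anti-secretory drug because of NSAID use counts as pharmacologically treated, with no NSAID term in any model.

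Three results are exposed: the contrast of pharmacological treatment with none, the time to initiation of any treatment, and the medical side of the surgical-versus-medical comparison. If NSAID use differs between levels of a predictor, that predictor's odds ratio for pharmacological treatment keeps part of the preventive use that the Methods set out to adjust for. The documents give no data on whether NSAID use differs in this way.

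**Working it through.** **Step 1: compare the texts.** The plan states no figure on this point, so the first check is which analysis names which class.

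| Analysis | Antithrombotics named | NSAIDs named |
|---|---|---|
| Descriptive comparison | yes | no |
| Logistic and multinomial | yes | no |
| Cox | yes | no |
| Poisson | no (no covariates listed) | no |
| Sensitivity analysis | yes | no |

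Antithrombotics are named in 4 of 5 analyses and NSAIDs in 0 of 5. NSAIDs appear once, in the retrieval sentence. That sentence lists the two classes separately under different ATC codes, and nothing defines antithrombotic treatment to include NSAIDs. An analyst following the covariate lists would code MB01A only.

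**Step 2: how large could the effect be?** Every input here is assumed.
- t = share treated for reasons other than NSAID prevention: 0.4 to 0.8.
- q = share of otherwise untreated NSAID users given prevention: 0.1 to 0.3.
- NSAID use across the two levels of a predictor with no true effect: 20% vs 30% (small contrast) up to 15% vs 45% (large contrast).
- Operated patients are set aside, t and q are the same at both levels, and there are no other covariates.

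At a level with NSAID share n, the treated share is p = t + n(1 − t)q. The predictor's odds ratio is [p₂/(1 − p₂)] / [p₁/(1 − p₁)]. The implied odds ratio for NSAID use itself is [t + (1 − t)q] / [t(1 − q)].

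- Lowest case, t = 0.8, q = 0.1, 20% vs 30%: p₁ = 0.8 + 0.2 × 0.2 × 0.1 = 0.804 and p₂ = 0.8 + 0.3 × 0.2 × 0.1 = 0.806. Odds ratio = (0.806/0.194)/(0.804/0.196) = 1.013. NSAID odds ratio = 0.82/0.72 = 1.14.
- Highest case, t = 0.4, q = 0.3, 15% vs 45%: p₁ = 0.4 + 0.15 × 0.6 × 0.3 = 0.427 and p₂ = 0.4 + 0.45 × 0.6 × 0.3 = 0.481. Odds ratio = (0.481/0.519)/(0.427/0.573) = 1.244. NSAID odds ratio = 0.58/0.28 = 2.07.
- In between, t = 0.6: with q = 0.1 and 20% vs 30%, (0.612/0.388)/(0.608/0.392) = 1.017; with q = 0.3 and 15% vs 45%, (0.654/0.346)/(0.618/0.382) = 1.168.

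**Step 3: how many of the pharmacological group would be prevention-only?** The share is n(1 − t)q / [t + n(1 − t)q], with overall NSAID use n of 0.1 to 0.3 (assumed).
- t = 0.4: 0.006/0.406 = 1.48% to 0.054/0.454 = 11.89%.
- t = 0.6: 0.004/0.604 = 0.66% to 0.036/0.636 = 5.66%.
- t = 0.8: 0.002/0.802 = 0.25% to 0.018/0.818 = 2.20%.

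**The case against.** The strongest reply is that the consequence is limited. Every patient has a GERD diagnosis with recent endoscopy, so many will have a GERD indication whatever else they take. Prior anti-reflux treatment, age, sex, Charlson index and year are already covariates and may absorb part of any NSAID-related difference. NSAID users who also take antithrombotics are partly covered. The regressions describe who receives which treatment, and no causal effect is claimed. All of this stands. It bears on size and not on the mismatch, because a covariate for earlier anti-secretory use is not a measure of NSAID use.

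A second reply is that every analysis naming a drug class names antithrombotics alone, so the omission may be deliberate. The documents cannot settle this. If it is deliberate, the stated reason for retrieving NSAIDs is wrong as it stands, and the two sections still need to be reconciled.

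Three stronger readings should be resisted.
- A reader might infer a much larger distortion, for example by taking a total NSAID odds ratio for treatment of about 4. At t = 0.6, an odds ratio of 4.17 needs 0.6 + 0.4q = 4.17 × 0.6 × (1 − q), so q = 1.902/2.902, about 66% of otherwise untreated NSAID users given prevention. The documents give no support for that, and it is far above the 10-30% assumed here.
- A reader might infer that adding NSAID use would remove the problem entirely. A baseline covariate misses prevention that starts after inclusion, while treatment is followed for two years.
- A reader might infer that NSAID users must be excluded. The stated purpose is to adjust, and exclusion goes beyond it.

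**Conclusion.** The mismatch is certain from the text: the plan retrieves two drug classes for one stated adjustment and carries through only one. The stated adjustment is therefore half done, and the sections should be reconciled before analysis.

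The size is unknown. Under the assumed inputs, a predictor with no true effect would show an odds ratio of about 1.01-1.24 for pharmacological treatment. That range is before any adjustment and is not what would remain in the planned models, whose covariates may absorb part of it. The prevention-only share of the pharmacological group would be 0.25-11.9%, or 0.7-5.7% if 60% are treated. The effect could thus be negligible or moderate. Nothing in the documents supports calling the surgical-versus-medical comparison invalid, and operations are identified independently of any of this.

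**What to change.** Add NSAID use (MM01A), measured before the endoscopy, beside antithrombotic treatment in the logistic, multinomial and Cox models and in the descriptive comparison. State the same exposure window for both classes. If NSAIDs are left out on purpose, correct the retrieval sentence in Methods and say why the data are obtained.

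The cost is one covariate from data already being retrieved. Its limit is that it reduces the problem without capturing prevention begun after inclusion, and the report should say so.

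Excluding users of either class can be offered as an optional further sensitivity analysis. With 10-30% users of each class, independent of each other (assumed), the planned exclusion leaves 70-90% of patients. Excluding both leaves 0.7 × 0.7 = 49% to 0.9 × 0.9 = 81%. If 60% had used an NSAID at some point in the six-year retrieval window (assumed), only 0.7 × 0.4 = 28% to 0.9 × 0.4 = 36% would remain. The exclusion also drops patients genuinely treated for GERD, and if later drug use counts, it selects on follow-up. It should therefore not replace the covariate.
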